9.4.2.2. Analysis Patient Reported Outcomes

Analysis to compare the subject reported effects of daprodustat and rhEPO on symptoms, health related quality of life, and health status, as discussed in Section 7.7, will be described in the RAP.

9.4.2.3. Safety Analyses

Safety data, including all AEs (i.e., non-serious, serious and AEs of special interest), laboratory data, SBP, DBP, HR, concomitant medications and meeting protocol defined safety stopping criteria (e.g., liver chemistry) will be descriptively summarized by treatment group. Reasons for stopping randomized treatment and for early study withdrawal will also be descriptively summarized by treatment group and time to stopping treatment or study will be presented graphically and assessed. Full details of all safety data reporting are described in the RAP.

[figure not shown]
9.4.3. Multiplicity Strategy

The multiplicity strategy for this trial will use a combination of a gatekeeper approach on the co-primary endpoints, followed by a closed-test multiplicity procedure wrapped around the family of superiority hypotheses consisting of MACE and the principal secondary endpoints.

Figure 2 illustrates the structure of the statistical testing plan. First, the co-primary endpoints will be evaluated for non-inferiority by comparing each two-sided 95% CI to the appropriate non-inferiority margin. Conditional on both co-primary endpoints achieving non-inferiority (i.e., passing the gatekeeper), the family of MACE and the principal secondary endpoints will be formally tested for superiority using the widely known Holm-Bonferroni procedure [Holm, 1979]. The procedure will be conducted based on a family-wise Type I error rate set at the one-sided 2.5% level. Details of the Holm-Bonferroni procedure will be fully described in the RAP.

Section 9.4.5 describes the planned interim analysis for the assessment of MACE futility. While this analysis will have a small impact on reducing the study-wise Type I error rate, there are no plans to adjust the alpha level used for end-of-study analyses. There are no prospectively defined plans to stop this study early for benefit.

Figure 2 Multiplicity controlled statistical testing plan

9.4.4. Covariates and Subgroups of Interest

The co-primary and principal secondary endpoints will be evaluated for a set of pre-specified subgroups to support the proposed indication. For the co-primary efficacy endpoint, these subgroups will be evaluated for both the primary ITT analysis of Hgb values during the EP regardless of adherence to treatment, as well as the sensitivity analysis limited to on-treatment Hgb values during the EP.

Although subgroup analyses aim to assess for consistency with the overall results, they may have low power, especially if the subgroup is small or has a low number of events. Statistical models will be adjusted for the covariates used in the original analysis, subgroup, treatment and treatment by subgroup interaction. Point estimates and two-sided 95% CIs will be estimated (presented on Forest Plots) and the subgroup by treatment interaction p-value calculated. Subgroup analyses will not be adjusted for multiplicity. Further subgroups/covariates may be defined in the RAP.

Category	Subgroups
Age	<65 years , ≥65 years - <75, ≥75 years
Gender	Female, Male
Race group	American Indian or Alaskan Native, Asian, Black, Native Hawaiian or Other Pacific Islander, White, Mixed Race
Ethnicity	Hispanic, non-Hispanic
Region	Appendix 3
Country	Appendix 3
Dialysis type	HD, PD (repeat using HD, HDF/HF, PD)
Dialysis vintage	0 to <2 years, 2 to <5 years, ≥5 years
Prior rhEPO dose	<7,000 U/week, ≥7,000 U/week
rhEPO Hypo-responsiveness	No, yes (see below for definition)
Baseline Hgb	<9, 9 to <10, 10 to 11, >11 g/dL
BMI	<30, ≥30 kg/m ²
Weight	< 75kg, ≥75kg
Baseline hsCRP	≤3 mg/L, >3 mg/L
United states	US, Non-US

rhEPO hypo-responder subgroup definition: rhEPO hyporesponders will be identified either by the ESA Resistance Index (ERI) [HERO study, [Johnson, 2015](#)] or by treatment at baseline with a very high dose of IV epoetin alpha. For each subject, baseline ERI will be calculated as the dry weight adjusted weekly mean ESA dose during the 8 week screening period divided by baseline Hgb concentration. Subjects with baseline ERI ≥ 2 U/kg/wk/g/L for epoetin-treated subjects; ≥ 0.008 $\mu\text{g}/\text{kg}/\text{wk}/\text{g}/\text{L}$ for darbepoetin-treated subjects and ≥ 0.01 $\mu\text{g}/\text{kg}/\text{wk}/\text{g}/\text{L}$ for methoxy-PEG-epoetin-treated subjects will be included in the pre-specified subgroup. In addition, subjects will be included if being treated at baseline with greater than or equal to the equivalent of 450 U/kg/week of IV epoetin alpha. This latter criterion covers subjects at higher body weight for which the ERI calculation is less accurate and is based on the NICE anemia guidelines of June 2015 [[NICE, 2015](#)]. Sensitivity analyses will explore alternative subgroup definitions: an ERI cut-point of ≥ 1.5 (or equivalent depending on ESA treatment) or using baseline prior rhEPO dose above the top 20th percentile for the study population.

rhEPO hypo-responder subgroup analysis plan: It is anticipated that approximately 10-15% of subjects may be classified as rhEPO hyporesponders according to this

definition, thus resulting in a subgroup size of potentially 300-450 subjects. The subgroup efficacy analysis will follow the same structure as that defined for the full study, assessing the comparative treatment effect in mean Hgb change between baseline and EP in subjects regardless of adherence to study treatment as well as in subjects who adhere to randomized treatment and using the same non-inferiority margin of -0.75 g/dL. For at least 90% power to demonstrate non-inferiority, 86 evaluable rhEPO hyporesponders are required per arm. The statistical model (ANCOVA) will include terms for prognostic randomization stratification factors, baseline Hgb, treatment, hyporesponder subgroup and treatment by subgroup interaction. Point estimates and two-sided 95% CIs will be generated to describe the treatment effect separately for rhEPO hyporesponders and the complement set of rhEPO non-hyporesponders; non-inferiority would be established if the lower limit of the two-sided 95% CI is greater than -0.75 g/dL. In addition, a nominal one-sided non-inferiority p-value and a nominal one-sided superiority p-value for the difference between the two groups will be generated.

While it is unlikely, given the sample size, that a sufficient number of adjudicated first MACE will occur to support a robust model-based analysis, subgroup analyses are planned for the co-primary MACE and principal secondary CV endpoints. The statistical analysis model (Cox Proportional Hazards) will include terms for prognostic randomization stratification factors, treatment, hyporesponder subgroup and treatment by subgroup interaction. Point estimates and two-sided 95% CIs for the hazard ratio will be generated to describe the treatment effect separately for rhEPO hyporesponders and the complement set of rhEPO non-hyporesponders; non-inferiority would be established if the upper limit of the two-sided 95% CI is less than 1.25. At a minimum, the incidence of MACE, its components and the principal secondary CV endpoints will be descriptively summarized by treatment group.

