9.1.2. Hgb efficacy Co-Primary Hypothesis

The co-primary Hgb efficacy objective will assess the estimand defined as the effect of daprodustat treatment relative to rhEPO on the change in Hgb from baseline to the average of all values in the EP, regardless of adherence to treatment including interruptions and discontinuations, the use of non-randomized ESA medication for any reason including rescue therapy, or the use of blood transfusions, in subjects on dialysis currently treated with an ESA with anemia secondary to CKD and assuming subjects do not die before the end of the EP. The analysis will test whether daprodustat is non-inferior to rhEPO according to the following statistical hypotheses:

- **Null:** The difference in mean change in Hgb between baseline and EP, between treatment arms (daprodustat -rhEPO), is less than or equal to -0.75 g/dL.

- **Alternative:** The difference in mean change in Hgb between baseline and EP, between treatment arms (daprodustat -rhEPO), is greater than -0.75 g/dL

The non-inferiority margin is pre-defined as -0.75 g/dL; determined based upon a combination of clinical judgment, statistical reasoning and regulatory guidance for designing non-inferiority trials.

Statistical significance of non-inferiority will be assessed at the one-sided 2.5% level. An ANCOVA model including prognostic randomization stratification factors (dialysis type and region), baseline Hgb and treatment will be used to obtain a point estimate and the two-sided 95% CI for the treatment difference (daprodustat -rhEPO) and generate the p-value for the non-inferiority test. The non-inferiority p-value will show strength of evidence against the null hypothesis. Non-inferiority will be established if the lower limit of the two-sided 95% CI for the treatment difference is greater than -0.75 g/dL.

The co-primary endpoints will be tested first. Non-inferiority needs to be established for both co-primary's to proceed to evaluate MACE for superiority as well as the principal secondary endpoints for superiority. Principal secondary endpoints include prioritized composites for MACE (including thromboembolic events and hospitalizations for HF) and IV iron utilization (defined as the average monthly IV iron dose used to Week 52). Statistical testing of MACE for superiority as well as the principal secondary endpoints will be adjusted for multiplicity (Section 9.4.3).

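### The hyporesponder Hgb non-inferiority decision rests on a CI from one all-subject ANCOVA, so its nominal 2.5% error holds only if hyporesponders have the same residual variance as everyone else

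*Protocol*

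**What the plan says.** Protocol section 9.4.4 gives hyporesponders their own definition, sample-size statement and analysis plan. On their number: "It is anticipated that approximately 10-15% of subjects may be classified as rhEPO hyporesponders according to this" definition, which the protocol puts at 300-450 subjects. On the analysis: "The subgroup efficacy analysis will follow the same structure as that defined for the full study", "using the same non-inferiority margin of -0.75 g/dL".

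The model is fixed: "The statistical model (ANCOVA) will include terms for prognostic randomization stratification factors, baseline Hgb, treatment, hyporesponder subgroup and treatment by subgroup interaction". From it, "Point estimates and two-sided 95% CIs will be generated to describe the treatment effect separately for rhEPO hyporesponders and the complement set", and a rule is attached: "non-inferiority would be established if the lower limit of the two-sided 95% CI is greater than -0.75 g/dL". The full-study rule that this mirrors is in section 9.1.2: "Statistical significance of non-inferiority will be assessed at the one-sided 2.5% level".

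Section 9.2.2 gives one SD for Hgb change, 1.5 g/dL, and derives 86 evaluable subjects per arm from it for 90% power. Section 9.4.4 carries the 86 over to hyporesponders unchanged. It mentions no hyporesponder SD, no group-specific variance and no robust standard error.

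The other subgroups in 9.4.4 use the same form of model ("Statistical models will be adjusted for the covariates used in the original analysis, subgroup, treatment and treatment by subgroup interaction"), but they feed forest plots and interaction p-values and have no stated decision rule.

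**The concern.** An ANCOVA, unless told otherwise, estimates a single residual variance from everyone in the model. The interaction term lets the treatment effect differ between hyporesponders and the rest, but not the scatter. With hyporesponders at 10-15% of subjects, the pooled variance mostly describes the other 85-90%, yet it sets the standard error for the smaller group. If hyporesponders vary more, their interval is too narrow and the rule passes too often. If they vary less, the interval is too wide and precision is wasted.

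At stake is one pre-specified conclusion, Hgb non-inferiority in hyporesponders. It is more than a line on a forest plot: 9.4.4 says the subgroup analyses are meant to support the proposed indication, and 9.4.5 lists efficacy in hyporesponders among the data the IDMC considers when judging futility.

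**Working it through.** **Inputs from the protocol.** Margin -0.75 g/dL, lower limit of a two-sided 95% CI, hyporesponder share 10-15% (9.4.4); SD 1.5 g/dL, expected difference 0, 30% non-evaluable (9.2.2); 1:1 allocation (4.1).

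**Assumed.** The ratio r of hyporesponder SD to the SD of the other subjects. The protocol does not give it, so a range is shown. The central share is p = 12.5%.

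**The plan's own figure.** With SD 1.5, margin 0.75, true difference 0 and one-sided 2.5%, the exact t calculation gives 90.3% power at 86 per arm and just under 90% (89.99%) at 85. The stated 86 is correct for SD 1.5. Applying it to hyporesponders assumes that SD for them too.

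**Width of the pooled interval.** Set the other subjects' variance to 1 and the hyporesponders' to r². The pooled variance is p·r² + (1 - p). The planned width divided by the correct hyporesponder width is

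ratio = sqrt(p·r² + 1 - p) / r

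At a true difference of exactly -0.75, one-sided false non-inferiority is 1 - Φ(1.96 × ratio).

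For p = 0.125:

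| r | p·r² + 1 - p | ratio | false non-inferiority |
|---|---|---|---|
| 0.8 | 0.955 | 1.22 | 0.8% |
| 1.0 | 1.000 | 1.00 | 2.5% |
| 1.2 | 1.055 | 0.86 | 4.7% |
| 1.3 | 1.086 | 0.80 | 5.8% |
| 1.5 | 1.156 | 0.72 | 8.0% |

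At shares of 10% / 15% the formula gives 4.8% / 4.6% for r = 1.2 and 8.3% / 7.7% for r = 1.5, so the share within the stated range matters little.

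**Simulation.**

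- An ANCOVA with treatment, subgroup, interaction and one baseline covariate (2,100 evaluable, 12.5% hyporesponders, 20,000 runs per setting) gave 2.6% / 4.7% / 5.8% / 7.9% at r = 1.0 / 1.2 / 1.3 / 1.5, and 0.6% at 0.8. Robust standard errors gave 2.4-2.6% throughout.
- The full stated model with dialysis type and region (3,000 subjects, 6,000 runs) gave 4.9% / 4.5% at r = 1.2 and 9.0% / 7.5% at r = 1.5, for shares of 10% / 15%. HC2 standard errors gave 2.3-3.0% and an ANCOVA within hyporesponders 2.1-3.0%, for r from 1.0 to 2.0.

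**What the correct interval costs.** Taking 30% off 300-450 leaves 210-315 evaluable hyporesponders, at least 105 per arm. Power at a true difference of 0, using the hyporesponders' own SD:

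| Hyporesponder SD | 86 per arm | 105 per arm | half-width at 105 |
|---|---|---|---|
| 1.5 | 90.3% | 95.0% | 0.406 |
| 1.8 | 77.5% | 85.2% | 0.487 |
| 2.25 | 58.5% | 67.2% | 0.609 |

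SDs of 1.8 and 2.25 are illustrations, 1.2 and 1.5 times the planning SD.

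**The case against.** **Variance not stated in the protocol.** Section 9.4.4 lists model terms and a decision rule. It does not say that the variance is common, and the analysis plan, which is not shown, could specify group-specific variances without contradicting a sentence of the protocol. That stands as a limit. But a named ANCOVA with no qualification is ordinarily fitted with one variance, and the protocol fixes both the model and the decision taken from it.

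**No evidence of unequal variance.** A reader might infer that hyporesponders are chosen for unstable Hgb and so must vary more. The documents do not support that. The definition rests on weight-adjusted ESA dose relative to Hgb, or on a very high epoetin dose, and neither measures instability. Design features point both ways. Subjects near the top dose step have less room for adjustment, which could widen the spread. The restricted entry Hgb, algorithmic titration, averaging over Weeks 28-52 and inclusion of values after rescue or transfusion could narrow it. The objection stands: a difference is possible but not established.

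**Nominal status.** A reader might also infer that the trial's type I error is inflated. It is not. Subgroup analyses are not multiplicity adjusted, the extra hyporesponder p-values are labelled nominal, and the analysis lies outside the gatekeeper and Holm-Bonferroni family of 9.4.3.

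**Worst-case point.** The error rates apply at a true difference of exactly -0.75, while the planned difference is 0. With 131 hyporesponders per arm, the pooled rule passes 1.6% / 2.3% / 3.7% of the time at a true -0.85 for r = 1.2 / 1.3 / 1.5, and 0.2% / 0.4% / 0.9% at -1.0. This is fair context, but the margin boundary is where a non-inferiority error rate is defined.

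**Conclusion.** The point holds as a conditional one. Read plainly, the hyporesponder interval has its nominal 95% coverage only if hyporesponders share the residual variance of the remaining subjects, and the protocol neither states nor supports that. With a 12.5% share and a true difference at the margin, false non-inferiority is 2.5% if the SDs are equal, 4.7% at a ratio of 1.2, 5.8% at 1.3 and 8.0% at 1.5. At 0.8 the rule is conservative, with a CI about 22% too wide. Which of these applies is unknown.

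Only the hyporesponder Hgb statement is exposed. The pooled variance is dominated by the other subjects, not wholly determined by them, and the formula allows for that. The point should not be stretched to every subgroup in 9.4.4, since the others carry no decision rule. This is a cheap improvement to a stated decision rule, not a threat to the trial's main conclusions.

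**What to change.** Add a sentence to 9.4.4: the Hgb CIs for hyporesponders and for the complement that are compared with -0.75 g/dL will use group-specific residual variances (a heterogeneous-variance ANCOVA, or an ANCOVA fitted within each group) or small-sample-corrected robust standard errors (HC2 or HC3).

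No new data are needed. If the variances are equal, the loss of precision is negligible with over 200 evaluable hyporesponders expected. If hyporesponders vary more, the interval is wider and power is below the stated 90% at 86 per arm, as tabulated above. That is the true precision of the comparison.

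Do not apply uncorrected robust standard errors to the sparse forest-plot subgroups, such as country or small race groups. In simulations with equal variances and 1.96 limits, they gave one-sided errors of 6.5-6.6% with 4 subjects per arm and 4.1-4.2% with 8 per arm, against 2.2% for the pooled model. HC3 stayed near nominal at 2.8%.

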9.4.5. Interim Analysis

The IDMC will periodically receive unblinded safety reports containing, at a minimum, clinical endpoints (whether adjudicated or pending adjudication) and SAEs, from an independent Statistical Data Analysis Center (SDAC) while the study is ongoing. The IDMC may recommend stopping the study for safety at any time.

In addition, the IDMC will evaluate the co-primary MACE endpoint to assess for futility of achieving non-inferiority at study completion. Pre-specified guidelines governing the decision to continue or stop the study will consider signals for harm, the predictive probability of achieving at least non-inferiority at trial end and the risk of incorrectly stopping for futility. In addition to MACE, any decisions regarding futility will take into account data related to: 1) components of MACE, 2) endpoints describing BP, 3) efficacy in rhEPO hyporesponders, 4) other safety and efficacy data across the daprodustat clinical program, 5) emerging data in the public domain pertaining to safety or efficacy of HIF-prolyl hydroxylase inhibitors, and 6) any other data considered to be relevant by the IDMC. The IDMC will make a recommendation to GSK and the ESC chair as outlined in the IDMC charter regarding whether the study should continue unchanged, be modified or be terminated.

There are no prospectively defined interim analysis planned to stop the study early for benefit. While the planned futility analysis will have a small impact on reducing study-wise Type I error rate, there are no plans to adjust the alpha level used for the final analysis.

Further details of futility rules and analysis timings will be provided in the IDMC Charter and RAP.

10. STUDY GOVERNANCE CONSIDERATIONS

10.1. Posting of Information on Publicly Available Clinical Trial Registers

Study information from this protocol will be posted on publicly available clinical trial registers before enrollment of subjects begins.

10.2. Regulatory and Ethical Considerations, Including the Informed Consent Process

Prior to initiation of a site, GSK will obtain favorable opinion/approval from the appropriate regulatory agency to conduct the study in accordance with ICH Good Clinical Practice (GCP) and applicable country-specific regulatory requirements.

The study will be conducted in accordance with all applicable regulatory requirements, and with GSK policy.

The study will also be conducted in accordance with ICH Good Clinical Practice (GCP), all applicable subject privacy requirements, and the guiding principles of the current version of the Declaration of Helsinki. This includes, but is not limited to, the following:

- IRB/IEC review and favorable opinion/approval of the study protocol and amendments as applicable
- Obtaining signed informed consent for each subject prior to participation in the study.
- Investigator reporting requirements (e.g. reporting of AEs/SAEs/protocol deviations to IRB/IEC)
- GSK will provide full details of the above procedures, either verbally, in writing, or both.

The IEC/IRB, and where applicable the regulatory authority, approve the clinical protocol and all optional assessments, including genetic research.

- Optional assessments (including those in a separate protocol and/or under separate informed consent) and the clinical protocol should be concurrently submitted for approval unless regulation requires separate submission.

- Approval of the optional assessments may occur after approval is granted for the clinical protocol where required by regulatory authorities. In this situation, written approval of the clinical protocol should state that approval of optional assessments is being deferred and the study, with the exception of the optional assessments, can be initiated.

10.3. Quality Control (Study Monitoring)

- In accordance with applicable regulations including GCP, and GSK procedures, PPD monitors will contact the site prior to the start of the study to review with the site staff the protocol, study requirements, and their responsibilities to satisfy regulatory, ethical, and GSK requirements.
- When reviewing data collection procedures, the discussion will also include identification, agreement and documentation of data items for which the eCRF will serve as the source document.

PPD will monitor the study and site activity to verify that the:

- Data are authentic, accurate, and complete.
- Safety and rights of subjects are being protected.
- Study is conducted in accordance with the currently approved protocol and any other study agreements, GCP, and all applicable regulatory requirements.

The investigator and the head of the medical institution (where applicable) agrees to allow the monitor direct access to all relevant documents

10.4. Quality Assurance

- To ensure compliance with GCP and all applicable regulatory requirements, PPD may conduct a quality assurance assessment and/or audit of the site records, and the regulatory agencies may conduct a regulatory inspection at any time during or after completion of the study.
- In the event of an assessment, audit or inspection, the investigator (and institution) must agree to grant the advisor(s), auditor(s) and inspector(s) direct access to all relevant documents and to allocate their time and the time of their staff to discuss the conduct of the study, any findings/relevant issues and to implement any corrective and/or preventative actions to address any findings/issues identified.

